# List of abbreviations

AE	Adverse Event
AC	Activity Curves
ADR	Adverse Drug Reaction
BC	Breast Cancer
CA	Competent Authority
CNS	Central Nervous System
e-CRF	Electronic Case Report Form
CRO	Clinical Research Organization
CRP	C-Reactive Protein
СТ	Computed Tomography
DSUR	Drug Safety Update Report
EC	Ethic Commitee
ECG	Electrocardiography
ECOG	Eastern Cooperative Oncology
EGF	Epidermal Growth Factor
EGFR	Epidermal Growth Factor Receptor
eGFR	estimated Glomerular Filtration Rate
ER	Estrogen receptor
FAS	Full Analysis Set
FDA	Food and Drug Administration
[  F]-FDG	18-fluorodeoxyglucose
GCP	Good Clinical Practice
GIST	Gastro Intestinal Stromal Tumour
GMP	Good Manufacturing Practice
GRP	Gastrin-Releasing Peptide
GRPR	Gastrin-Releasing Peptide Receptor
Hb	Hemoglobin
HCI	Hydrogen Chloride

HPLC	High-Performance Liquid Chromatography
HR	Heart Rate
ICF	Informed Consent Form
ICH	International Conference on Harmonization
ICRP	International Commission on Radiological Protection
IEC	Independent Ethics Committee
IHC	Immunohistochemistry
IMP	Investigational Medicinal Product
IRB	Institutional Review Board
ISF	Investigator Site File
ITLC	Instant Thin Layer Chromatography
ITT	Intention To Treat
LN	Lymph Node
LPLV	Last Patient Last Visit
MBq	Mega Becquerel
MIRD	Medical Internal Radiation Dose
MedDRA	Medical Dictionary For Regulatory Activities
MRI	Magnetic Resonance Imaging
NCI	National Cancer Institute
NMB	Neuromedin B
NOAEL	No Observed Adverse Effect Level
NSCLC	Non–Small Cell Lung Cancer
PC	Prostate Cancer
PET	Positron Emission Tomography
p.i.	Post injection
PI	Principal Investigator
PK	Pharmacokinetics
PP	Per Protocol
PT	Prothrombin Time
PTT	Partial Thromboplastin Time

A005D-E01-201	Page 10 of 73	

## **Study Protocol**

PV	Pharmacovigilance
PT	Preferred Term
QA	Quality Assurance
QC	Quality Control
QTc	frequency-corrected QT-time
RBC	Red Blood Cell
RCP	Radiochemical Purity
ROI	Region of Interest
RR	Respiratory Rate
SAE	Serious Adverse Event
SAP	Statistical Analysis Plan
SD	Standard Deviation
SOC	System Organ Class
SOP	Standard Operating Procedure
mSv	milliSievert
SUSAR	Suspected Unexpected Adverse Reaction
SUV	Standardized Uptake Value
TAC	Time Activity Curve
TBR	Target to background ratio
ткі	Tyrosine-Kinase Inhibitor
TMF	Trial Master File
WBC	White Blood Cell
WHO	World Health Organization
VOI	Volume Of Interest

# Definitions

### • Pre-screening:

The pre-screening is the period before the signature of the Informed Consent Form (ICF).

### Screening:

The screening period starts at the time of signature of ICF and ends on the day of IMP injection.

### • Enrollment:

A subject is enrolled when he/she is administered with the Investigational Medicinal Product (IMP).

### • IMP phase:

The IMP phase starts when IMP is administered to a subject, i.e. if a subject has entered the IMP phase, it means this subject has been injected with [Ga]-NeoBOMB1.

### • Screening failure:

A screening failure occurs when a subject who has signed the ICF (i.e. screened/enrolled subject) does not enter the IMP phase (i.e. injected subject).

# 1 Study Synopsis

Version date	July, 05 th , 2018	CT Number: 2017-003432-37
version date	July, 05  , 2016	
Study number	A005D-E01-201	Clinical phase: II
Investigational	[68Ga]-NeoBOMB1 50	) µg, kit for radiopharmaceutical preparation
Medicinal Product		
Title of the study	Phase II study of pre	liminary diagnostic performance of [68Ga]-NeoBOMB1
	in adult patients with	malignancies known to overexpress Gastrin Releasing
	Peptide Receptor.	
Study centres	Multi-center study	
Sponsor	Advanced Accelerato	r Applications
Potential Indication	Diagnosis and or mor	nitoring of tumours known to overexpress GRPR.
Rationale	numerous central and receptor (GRPR), it a chain reactions. Besi demonstrated to be a may be involved in gr In fact, upregulation including breast, pro stomach, pancreas, u	ke peptide growth factor implicated in the regulation of a peripheral functions. By binding to a GRP extracellular activates an intracellular G-protein that triggers further ide its physiological widespread role, GRP has been a potent mitogen for normal and neoplastic tissues and rowth dysregulation and carcinogenesis. of GRP/GRPR has been reported in several cancers, ostate, colon, lung (small cell and non-small cell), uterus, ovaries, head and neck squamous cell cancer I nervous system malignancies.
	metastatic breast ca overexpression was i	expression has been investigated in primary and ancer among different molecular subtypes. GRPR most strongly associated with estrogen receptor (ER) n over 75% of the primary tumour samples and in over tic lymph nodes.
	in prostate tissues that transformation (i.e. pr GRP receptors have	GRP receptor overexpression has been demonstrated at are already neoplastic or in the process of malignant ostatic intraepithelial neoplasias). In this specific case, been thought of as markers for early molecular events nesis and useful in differentiating prostate hyperplasia sia.
	is responsible for lung also been reported in	been found in the pulmonary neuroendocrine cells and g development and maturation. Nevertheless, GRP has relation to growth dysregulation and carcinogenesis on ancer (NSCLC) proliferation. In fact, increased levels of

	
 
GRP have led to increased release of pro-ligands for epidermal growth factor receptor (EGFR) with subsequent activation of EGF and mitogen-activated protein kinase downstream pathways.
 
Presence of GRP and/or expression GRPR have also been investigated in colorectal cancer samples (primary tumour, lymph nodes and metastatic lesions) where over 80% samples expressed GRP/GRPR as opposed to adjacent normal healthy epithelium.
 
Overall, the literature accounts with a growing body of evidence suggesting that GRPR might be a valuable target.
 
Peptide receptor agonists have long been the ligands of choice for tracer development and utilization in nuclear medicine thanks to their high radioactive accumulation inside the target cells after receptor-radioligance complex internalization. However, GRPR antagonists have been compared to GRPR agonists and showed greater tumour uptake and better image contrast. Furthermore, GRPR antagonists allow for a safer clinical use, since page against adverse offecte are expressed.
 
	
Objectives	no acute biological adverse effects are expected. The Sponsor has therefore designed the current protocol to establish whether the ligand NeoBOMB1, a high affinity antagonist for GRPR, radiolabelled with a well-established PET isotope, Gallium-68 (  Ga) is a suitable radiotracer for in vivo detection of GRPR-expressing malignancies, currently focusing on breast, prostate, lung (small cell and non-small cell) and colon-rectum.	
Objectives	
 
Primary Objective 
 
To characterize preliminary targeting properties of [Ga]-NeoBOMB1 in patients with malignancies known to overexpress GRPR.
 
 
 
Secondary objectives 
 
To assess safety and tolerability of a single diagnostic dose of [Ga]-NeoBOMB1 administered as an intravenous bolus injection.
 
To assess the bio-distribution, pharmacokinetics, radiation dosimetry, and absorbed doses in critical organs for [Ga]-NeoBOMB1 in a limited set of patients.
 
To establish the optimal threshold, expressed as Standardized Uptake Value (SUV), to discriminate Positron Emission Tomography (PET) imaging positive results from negative ones.
 
To estimate the [Ga]-NeoBOMB1 PET imaging performance lesion-based and patient-based relative to a comparable standard imaging practice (eg PET, CT) according to the tumour type.
 
To estimate the [Ga]-NeoBOMB1 PET diagnostic performance lesion-based and patient-based relative to the GRPR histopathology
 
 
 
	

	findings (e.g. IHC)
Study design	
 
This is a Phase II, multi-center, open label, single dose study in patients with tumour types known to overexpress GRPR, including breast, prostate, colorectal, non-small cell lung (NSCL) and small-cell lung (SCL) cancer. Population will be divided into two groups:
 
a Phase-II dosimetry group, accounting with 10 patients (splitted into breast cancer: n=5 female patients and prostate cancer: n=5 male patients) who will undergo several assessments to confirm previous data on tracer bio-distribution, radiation dosimetry, residence time for critical organs, and absorbed dose critical organs for [Ga]-NeoBOMB1. Venous whole blood and urine samples will be collected for activity-based pharmacokinetics characterization;
 
a Phase-II non-dosimetry group, accounting with 40 patients splitted into :         
 
✓ Breast cancer: n=5
 
✓ Colorectal cancer: n=5
 
✓ Colorectal cancer: n=10.
 
 
 

	$\checkmark \text{ NSCLC: } n=10$
PET Imaging Data	
 
✓ SCLC: n=10
 
Patients included in the non-dosimetry group will undergo one early and one late whole-body PET-imaging acquisition, with no blood and urine sampling. Only prostate tumour patients will undergo an additional early 5-min static PET scan to better assess lymph node metastases (if applicable). GRPR expression must be assessed while the study is ongoing within 4 weeks after IMP injection by Immunohistochemistry staining from archival or recent biopsy specimens (not older than 6 months prior to IMP injection). The objectives of the study will be applicable for the whole study population with the exception of the secondary objective relative to the biodistribution and dosimetry that will be applicable only for the dosimetry group.
 

PET Imaging Data	The subjects enrolled in the dosimetry group will undergo 4 15-min static whole body PET scaps at 15 min, 1b+15 min, 2b+15 min, and at 4b+30 min
acquisition	
 
whole-body PET scans at 15 min, 1h±15 min, 2h±15 min and at 4h±30 min post injection (p.i.) to determine absorbed doses to normal organs and to target tumour lesions. Regions of Interest (ROIs) or Volumes of Interest (VOIs) will be drawn on the late whole-body PET images over the critical organs and tumour lesions to generate tissue time-activity curves (TACs), calculate the tumour-background ratio and assess the radioactivity residence times.
 
To determine blood activity curves, venous whole blood samples will be withdrawn (around 0, 5, 10, 20, 30, 60 min, 2 h and 3-4 h p.i.) and assessed
 

	via γ-counter for radioactivity measurements. Urine samples from 0-2 h and from 2-4 h p.i. will be collected and assessed via γ-counter for radioactivity measurements to complete dosimetry and biodistribution assessments. Urine samples will be saved, frozen for further metabolite assessments, at the Sponsor's decision. The subjects enrolled in the Phase II non-dosimetry group will undergo whole-body PET acquisitions at 1h30±30min and at 2h30±30min, likely to be a 15-min static PET for all tumour-types combined with a 5-min-static early-PET for prostate cancer.			
CT Imaging Data Acquisition	For all patients a low-dose CT will be combined to PET imaging.			
	Desimetry group:			
Data analysis,	Dosimetry group:			
biodistribution and	ROIs/VOIs for critical organs and tumour lesions will be drawn using the			
dosimetry	acquired static PET images resulting in tissue TACs with quantitative			
	fractions of administered activity. ROIs/VOIs will be drawn over these organs			
	to determine relative radiotracer uptake calculated as a percentage of the			
	injected dose per gram of tissue (%ID/g). Tissue TACs will be generated from			
	the amount of radioactivity in one given tissue considering renal excretion			
	activity.			
	Tissue TACs will be fitted to mono- and bi-exponential curves to yield			
	cumulative activities and residence times will be calculated.			
	Dosimetry calculations will be issued from the analyses of organs receiving			
	the highest dose, identified visually. Urine samples from 0-2h and from 2-4h			
	post-injection will be collected to complete dosimetry and biodistribution			
	assessments.			
	The absorbed dose (µGy/MBq) will be transformed into formal			
	biological equivalent dose for radiation exposure (µSv/MBq) to finally yield			
	an effective radiation dose, a factor between others that could help providing			
	· · · •			
	an estimation of total danger to the whole organism.			
	All patients:			
	Maximum standardized uptake values (SUV max ) will be used to determine the			
	tumour lesions, defined as focal areas of abnormal uptake featuring greater			
$SUV_{max}$ than that of surrounding tissue. The imaging time				
	characterized by the greatest number of lesions will be identified via qualitative visual analysis. Similarly, the greatest SUV values will be determined for each lesion on all scans via semi-quantitative analysis. Malignant-like lesions compatible per tumour type and localisation will be semi-quantified and expressed as SUV mean and SUV max . All lesions will be			
	counted and analyzed by measuring SUV mean and SUV max and relative			
	background.			
	Clinical assessment (surgery, imaging or physical examination) during 3			
	months after IMP injection will be collected if available for patients to			

A005D-E01-201	Page 16 of 73
A005D-E01-201	Page 16 of 73

	correlate the focal uptake of [  Ga]-NeoBOMB1 PET which was not possible be matched to morphological lesions on CT/MRI.			
Safety	Safety assessments including physical examination, vital signs, Electrocardiogram (ECG) with frequency-corrected QT-time (QTc) assessment, routine blood analysis and urinalysis will be performed prior to [  Ga]-NeoBOMB1 administration on all subjects.			
	Dosimetry group: twelve-lead ECG readings and vital signs will be checked pre-dose, immediately after the radiotracer administration, at 30 min, after the last whole-body scan (around 4h) and during the FU visits scheduled at Day 2 (24h p.i.), Day 7±1, and Day 14±2 for physical examination, routine blood analysis, urinalysis, vital signs and ECG.			
	Non-dosimetry group : twelve-lead ECG readings and vital signs will be checked at pre-dose and at 30 min after the administration. At Day 2, the FU visit will be a phone call to assess potential adverse events, allergic reactions and concomitant treatments. The FU visits of Day 7±1 and Day 14±2 account for physical examination, routine blood analysis, urinalysis, vital signs and ECG. Visit at Day 7±1 is optional and can be replaced by a phone call to only assess potential adverse events, allergic reactions and concomitant treatments.			
	The emergence of any Adverse Event (AE) and Serious Adverse Event (SAE) will be monitored and recorded during trial conduct. Adverse events will be graded per the Toxicity Grading Scale in vaccine clinical trials.			
Tracer	
 
NeoBOMB1 will be radiolabelled locally following a predefined procedure using a solution of Ga in hydrochloric acid (HCl) provided by a Ge/Ga generator to obtain [Ga]-NeoBOMB1 as radiolabelling imaging product for intravenous injection.
 
The dose of [Ga]-NeoBOMB1 to be injected is 3MBq/kg ±10%, no less than 150 MBq and no more than 250 MBq. This amount of radioactivity is sufficient for Quality Control (QC) testing and quality imaging with [Ga]-NeoBOMB1.
 
			
	[  Ga]-NeoBOMB1 will be administered according to applicable regulation (including local regulations, International Commission on Radiological Protection (ICRP) Publication 62 and Radiation protection 99).			
Planned number of	Fifty patients bearing malignancies known to overexpress GRPR originating			
subjects	from either breast, prostate, lung (small-cell and non-small cell) or colon-			
	rectum will be enrolled. Population will be divided into 2 groups: the			
	dosimetry group will include 5 patients with breast cancer and 5 patients with prostate cancer, who will undergo further assessments for dosimetry			
	calculations.			
	The non-dosimetry group will include 40 patients. Patients will be splitted into			
	: ✓ Breast cancer: n=5			

	✓ Prostate cancer: n=5
	✓ Colorectal cancer: $n=10$ .
	✓ NSCLC: n=10
	✓ SCLC: n=10
Inclusion and	Main Inclusion Criteria
exclusion criteria	
	1. Subjects must be at least 18 years of age
	2. Subjects must have signed and dated an informed consent prior to
	any study-specific procedures.
	3. Subjects with histologically-confirmed tumour, for whom a less than
	6-month-old biopsy has been performed.
	4. Dosimetry group:
	Luminal breast cancer
	Adenocarcinoma of the prostate
	5. Non-dosimetry group:
	Luminal breast cancer
	Adenocarcinoma of the prostate
	Small-cell lung cancer
	Non-small cell lung cancer
	Colorectal carcinoma
	
 
At least one malignant lesion detected via functional or morphological imaging (PET combined to appropriate tracer according to tumour type, CT, MRI) within 3 months prior to the administration of [Ga]- NeoBOMB1.
 

	
 
The Eastern Cooperative Oncology (ECOG) performance status 0-
 
2.
 

	
 
Subjects must agree to use highly effective methods of contraception (female partners of male participants should use highly effective methods of contraception) during the trial.
 

	Main Exclusion Criteria
	1. Renal insufficiency or an estimated Glomerular Filtration Rate (eGFR) <50 ml/min/1.73m  .
	
 
Haematological toxicity grade > 2 (Toxicity Grading Scale in vaccine clinical trials)
 

	3. Participation in any other investigational trial within 30 days of study entry.
	4. Subjects with positive pregnancy test (Urine dipstick), and/or currently breast-feeding
	5. Concurrent severe illness or clinically relevant trauma within 2 weeks before the administration of the investigational product that might preclude study completion or interfere with study results.
	
 
Concurrent bladder outflow obstruction or unmanageable urinary incontinence.
 

A005D-E01-201		Page 18 of 73	
Study Protocol			

T

	7. Known or expected hypersensitivity to  Gallium, NeoBOMB1, or any			
	excipient present in [  Ga]-NeoBOMB1.			
	8. Any condition that precludes raised arms position			
	9. Prior administration of a radiopharmaceutical within a period			
	corresponding to 8 half-lives of the radionuclide.			
	10. History of somatic or psychiatric disease/condition that may inte			
	with the objectives and assessments of the study.			
Study duration and	The study will have a duration of approximately 6 weeks, with a pre-injection			
Assessments	phase of 4 weeks, including the screening/baseline assessment period, the			
	injection and PET visit on Day 1, 3 safety follow-up visits post-administratio			
	of investigational drug on Day 2, Day 7±1 and Day 14±2. If available, data			
	generated from routine clinical disease follow-up assessments within 3			
	months from IMP injection will be collected.			
	The study assessments are described in the Visits Schedules and			
	assessment, section 4.5.			
Study periods	A) The Screening period will last 28 days (Day -28 to -1) or less per			
	subject and includes the Screening Visit to obtain informed consent			
	and establish protocol eligibility.			
	B) The injection and PET day is [68Ga]-NeoBOMB1 administration day			
	(Day 1) and differs according to groups. For the dosimetry group, it			
	includes 7 time-points: pre-dose, 0-5 min, 5-15 min, 30 min, 1h, 2h, 3-			
	4h p.i For the non-dosimetry group, it includes 4 time-points: pre-			
	dose, injection (0-5 min), 1h30±30min p.i . and 2h30±30 min p.i.			
	C) The safety follow-up period lasts for 14 days from PET day. It inclu			
	FU visits on Day 2, Day 7±1, and Day 14±2 for all subjects.			
	D) The optional routine clinical follow-up will start on D14±2 follow-up			
	visit and will last up to 3 months from IMP injection according to clinical			
	disease assessment.			
Statistical methods	All statistical analyses will be primarily descriptive in nature and will include			
	summaries and graphical presentations of data. All data presentations will			
	be presented by the overall population but may also be repeated split by			
	tumour type where relevant. Some presentations will also be repeated split			
	by whether or not the patient was found to have tumours bearing GRPR			
	expression according to cytology and/or histopathology findings.			
	The preliminary targeting properties of [68Ga]-NeoBOMB1 will be assessed			
	by summaries of number and location of lesions identified by PET, SUV			
	values per lesion, tumour background ratio of [68Ga]-NeoBOMB1 and the			
	percentage of injected dose reaching the target presented split by GRPR			
	positive and negative patients. Tumour uptake will be evaluated by Standard			
	Uptake Value. SUV mean and SUV max will be determined and summarized			
	descriptively.			
	Adverse events will be listed on an individual basis and summarized by			
	System Organ Class and Preferred term including relationship and severity.			

Γ

Clinical laboratory parameters, vital signs, and ECG parameters will be summarized and presented graphically as observed values and changes form baseline at each measuring time. Clinical laboratory parameters will also be analysed in terms of tabulations of values to within, below or above normal ranges provided by the laboratory of each site. Descriptive statistics and graphical presentations will be produced for bio- distribution, radiation dosimetry data as appropriate. Number of observed tumour lesions and localization in PET/CT will be compared to number of observed lesions and localization in a comparable conventional imaging by GRPR positive and negative patients. Positive and negative lesions by the two imaging techniques will be cross tabulated overall and by localization area on a lesion level and a patient level and overall, positive and negative sensitivity agreement calculations and tests of association will be performed where appropriate overall and split by GRPR positive and negative patients. This will also be repeated splitting by primary tumour type of patients in the trial. The preliminary diagnostic performance of [  Ga]-NeoBOMB1 relative to cytology and/or histopathology findings from archival and/or recent biopsy specimens will be assessed primarily on a patient level, but also on a lesion level for lesions with associated biopsy data available. Sensitivity and specificity calculations will be performed by cross tabulating GRPR positive or negative patients according to cytology
--

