# 3 Study design

# 3.1 Description of the study

## Rationale of the design:

This is a Phase II, multi-center, open label, single dose study in cancer patients with tumour types known to overexpress GRPR, including breast, prostate, colorectal, small-cell and non-small cell lung.

[figure not shown]
The main objective of the Phase II study is the characterization of the preliminary targeting properties of [Ga]-NeoBOMB1 in patients with malignancies known to overexpress GRPR to assess the tumour-background ratio. The secondary objectives of the clinical trial are safety and tolerability and dosimetry aspects. All the objectives, with the exception of the secondary one relative to biodistribution and dosimetry that will be assessed within the dosimetry group, will be assessed in the overall population (n=50). Analyses of the dosimetry group data will

lead to the optimal time window for PET/CT imaging for future clinical trials. However, in the case that the Sponsor obtains the results of the dosimetry and biodistribution assessments from at least 3 patients of the dosimetry group before the full completion of the study recruitment and the results show that the optimal time window is different from 1h30±30min or 2h30±30min as initially predicted by the Sponsor, the timepoints of the whole-body PET/CT scans for the remaining patients included in the non-dosimetry group will be adjusted.

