# 3.3 Study Endpoints

- 3.3.1 Primary Study Endpoint
  - Number and location of tumour lesions detected by [Ga]-NeoBOMB1 overall and for each tumour type
  - Calculation of the ratio tumour/background SUV and calculation of percentage absorbed dose in tumour overall and for each tumour type.
- 3.3.2 Secondary Study Endpoints
  - Standard safety parameters (clinical monitoring, laboratory, ECG)
  - Tolerability and safety of the administration of a diagnostic dose of [Ga]-NeoBOMB1 in patients with malignancies known to overexpress GRPR as determined by absence of:
    - increased number of SAEs compared to other peptide-based radiotracers;
    - clinically relevant changes of physiological parameters (blood pressure, heart rate, ECG findings)
  - Generation of decay corrected tissue TACs from [Ga]-NeoBOMB1 PET/CT images in normal organs, tumour lesions.
  - Quantification of urinary excretion of [Ga]-NeoBOMB1
  - Calculation of half-life of [Ga]-NeoBOMB1 in blood
  - Generation of non-decay-corrected TACs from [Ga]-NeoBOMB1 PET/CT images in normal organs, tumour lesions
  - Calculation of residence times in organs and tumour lesions of [Ga]-NeoBOMB1
  - Calculation of absorbed doses and effective whole body dose of [Ga]-NeoBOMB1
  - Calculation of the SUV of each lesion
  - Number and location of tumour lesion detected by [Ga]-NeoBOMB1 in comparison with comparable standard imaging modalities such as FDG-PET

- Calculation of the [Ga]-NeoBOMB1 PET overall, positive and negative agreement on a lesion-by-lesion basis as well as on a patient basis relative to the standard imaging overall and for each tumour type
- Comparison of number of patients with tumour lesions detected and number of tumour lesions detected by [Ga]-NeoBOMB1 with cytology and/or histopathology from archival and/or recent biopsy specimens
- Calculation of the [Ga]-NeoBOMB1 PET sensitivity and specificity on a lesion-bylesion basis for all lesions with associated biopsy data, and on a patient basis relative to histopathology / cytology data

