# 7.3 Efficacy Analysis

### Primary endpoint:

• The preliminary targeting properties of [Ga]-NeoBOMB1 will be assessed by summaries of the number and location of lesions identified by PET, SUV values per

lesion, tumour background ratio of [Ga]-NeoBOMB1 and the percentage of injected dose reaching the target presented split by GRPR positive and negative patients. Tumour uptake will be evaluated by Standard Uptake Value. SUVmean and SUVmax will be determined and summarized descriptively.

• The tumour-background ratio of [Ga]-NeoBOMB1 and the percentage of injected dose reaching the target will be calculated using the acquired images resulting in time-activity curves (TACs) with quantitative fractions of administered activity and summarized descriptively.

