#### 7.2 Evaluation of Targeting Properties by Standard Uptake Value (SUV)

Targeting properties of [Ga]-NeoBOMB1 will also be evaluated by PET imaging using tumor uptake. Tumor uptake will be evaluated by the Standard Uptake Value (SUV) at each lesion by PET Imaging. The maximum SUVmean and SUVmax (g/mL) of each lesion will be presented by the lesion location with summary statistics (n, mean  $\pm$  standard deviation, minimum, median, quartiles, and maximum) at scheduled time points overall and split by GRPR positive and negative patients, as well as by tumor type. Dosimetry and non-dosimetry group will be summarized separately due to different scheduled time points.

The 80% and 95% confidence intervals for difference in SUV (SUVmean and SUVmax) between GRPR positive and negative patients will be derived by Student's *t* distribution if normality assumption is adequate, or Wilcoxon Rank Sum method otherwise.

The Standard Uptake Value ratio (SUVr) at each time point will be calculated as the SUVmean of each lesion / the SUVmean of different regions as a reference and presented in a data listing.

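### As written, known lesions without a PET focus contribute no uptake value, so the SUV summaries are conditional on detection and biased upward, most for weakly targeted tumour types

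*Protocol*

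**What the plan says.** **Which lesions are measured.** The data-analysis part of the protocol synopsis, under all patients, uses SUVmax to determine "tumour lesions, defined as focal areas of abnormal uptake featuring greater" SUVmax "than that of surrounding tissue". SUVmean, SUVmax and relative background are then measured on the lesions so found, and "the greatest SUV values will be determined for each lesion on all scans via semi-quantitative analysis". For the dosimetry group, regions are "drawn on the late whole-body PET images over the critical organs and tumour lesions to generate" time-activity curves.

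**What is summarised.** One primary endpoint in Protocol 3.3.1 is "Calculation of the ratio tumour/background SUV and calculation of percentage absorbed dose in tumour overall and for each tumour type", and Protocol 3.1 gives the purpose of the main objective as "to assess the tumour-background ratio". Protocol 7.3 assesses targeting by "summaries of the number and location of lesions identified by PET, SUV values per" lesion, together with the tumour/background ratio, split by GRPR status. SAP 7.2 says "Tumor uptake will be evaluated by the Standard Uptake Value (SUV) at each lesion by PET Imaging". It summarises these values by tumour type and GRPR status and adds 80% and 95% confidence intervals for the SUV difference between GRPR-positive and GRPR-negative patients.

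**What happens to the rest.** SAP 5.4 uses observed values only unless otherwise stated. Neither document says to place a region on a known lesion that shows no focus, or assigns such a lesion a value. The reverse case is covered: Protocol 4.4 collects later clinical data to interpret PET foci that have no match on CT or MRI.

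**The concern.** A tumour that takes up no tracer produces no focus, hence no SUV and no ratio. The summaries then describe how hot the visible lesions are and leave out how the tracer behaves across all known lesions. The second question is what characterising targeting by tumour type needs.

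Lesions without uptake cannot be assumed rare. In Protocol 2.3.1, a gallium-labelled antagonist showed specific uptake in 5 of 9 prostate and 4 of 8 breast cancer patients, and an agonist found 8 of 30 GIST lesions against 25 of 30 by FDG. These are other tracers, but Protocol 7.1 itself expects some GRPR-negative patients.

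Three results are affected: the SUV summaries by tumour type, the GRPR-positive/negative confidence intervals, and the secondary objective of an SUV threshold separating positive from negative PET results. That last objective needs SUVs from known lesions that PET does not show, and the written rule does not generate them.

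**Working it through.** **The plan's own figure.** Protocol 7.1 and SAP 10 give one interval: 25/30 = 83.3%, 95% CI 66.4% to 92.7%. The Wilson formula with z = 1.96 has centre (p + z²/2n)/(1 + z²/n) = 0.7955 and half-width 0.1311, giving 66.4% to 92.7%. It reproduces, but it concerns patient-level sensitivity and is not an input here. The documents give no expected SUV, ratio or spread, so everything below is an illustration on stated assumptions.

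**Check 1: SUV by tumour type.** Assume log-normal lesion SUV with geometric SD 2 (s = ln 2 = 0.693), true median m = 6 for a strongly and m = 2 for a weakly targeted type, and a lesion visible when SUV > c.

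- Share visible: d = Φ(ln(m/c)/s)
- Median among visible lesions: m × exp{s × Φ⁻¹(1 − d/2)}

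For m = 2 and c = 3: ln(2/3)/0.693 = −0.585, so d = 0.28; Φ⁻¹(0.86) = 1.08; visible median = 2 × exp(0.75) = 4.2.

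| Cut-off c | Strong type: visible, median | Weak type: visible, median | Reported ratio (true 3.0) |
|---|---|---|---|
| 1 | 99.5%, 6.0 | 84%, 2.3 | 2.6 |
| 2 | 94%, 6.3 | 50%, 3.2 | 2.0 |
| 3 | 84%, 6.9 | 28%, 4.2 | 1.6 |

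The direction is the same in each row. The size depends on the cut-off, which the documents do not state as a number.

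**Check 2: the protocol's relative rule.** Let the lesion-to-surrounding SUVmax ratio be log-normal and let a lesion enter only if its ratio exceeds 1. The same formulas apply with c = 1. With SD of log 0.7:

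| True median ratio | Share entering | Median among those entering |
|---|---|---|
| 0.5 | 16% | 1.33 |
| 0.8 | 38% | 1.49 |
| 1.0 | 50% | 1.60 |
| 1.5 | 72% | 1.93 |
| 3.0 | 94% | 3.16 |

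The contrast of 3.0 with 0.5 is truly 6-fold and is reported as 3.16/1.33 = 2.4-fold. With SD of log 0.4 it is 3.00/1.13 = 2.7-fold, and with 1.0 it is 3.56/1.60 = 2.2-fold. Strong types barely move; weak types are inflated.

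**Check 3: does the SAP's ratio have to exceed 1?** SUVr in SAP 7.2 is lesion SUVmean over the SUVmean of unspecified reference regions. Assume lesion mean 0.6 of its maximum, local tissue mean 0.8 of its maximum, true median SUVmax ratio 1.0 and SD of log 0.7. Simulating 1,000,000 lesions, the share of detected lesions with SUVr at or below 1 is 0%, 32%, 68% and 95% when the reference-region mean is 0.5, 1.0, 1.5 and 3.0 times local tissue. So SUVr need not exceed 1.

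**The case against.** **Low detection would be visible elsewhere.** Number and location of lesions, by tumour type, is also a primary endpoint, and SAP 7.1 compares it with conventional imaging. SAP 7.4.1 computes lesion-level positive agreement, whose denominator includes lesions the tracer missed; SAP 7.4.2 gives patient-level agreement over all patients; SAP 7.5.3 plots the proportion of conventional lesions detected. This stands. A reader might infer that a weakly targeted type would pass as well targeted. The documents do not support that, because these tables would show the low detection, and in the illustrations the weak type still reads below the strong one. The tables do not, however, change the SUV values.

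**The ratio is not forced above 1 in general.** A reader might infer that it is. That is strictly true only for lesion SUVmax over surrounding-tissue SUVmax. The protocol's primary ratio names neither SUV metric nor background region, and SUVr in the SAP can fall below 1 and goes only into a listing (SAP 7.2 and 11). This stands.

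**The exclusion is inferred from silence.** SAP 7.4 and 7.5.1 speak of negative as well as positive lesions, and a threshold objective hardly makes sense without SUVs from negative sites. Protocol 4.1.6 refers to a separate central reading manual, which is not among the documents. It may contain a rule; if so, the SAP should state it.

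**The GRPR bias works against the tracer.** Truncating the GRPR-negative group from below narrows the contrast. That is conservative for showing specificity, but the interval is still distorted.

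**Known-lesion measurement has its own error.** Conventional imaging may be three months old (Protocol 3.4.1), systemic treatment may continue (Protocol 5.4), and localisation relies on low-dose, non-enhanced CT (Protocol 4.5). This is a good reason not to make all-lesion values the sole primary summary. It does not argue against reporting them alongside.

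**Conclusion.** The point holds in a limited form. Followed as written, the lesion definition, SAP 7.2 and the observed-values rule leave known lesions without a focus out of the SUV and tumour/background values. The uptake summaries are then biased upward, most for weakly targeted types, and differences between tumour types and between GRPR groups are compressed. No other analysis in the plan supplies the missing values, and the threshold objective lacks SUVs from PET-negative lesion sites.

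The size is not known. Under the log-normal assumption with geometric SD 2 and medians 6 and 2, a true ratio of 3.0 is reported as about 2.6 to 1.6 for cut-offs of 1 to 3. The study is descriptive and the detection tables limit the scope for misreading, so this is an inexpensive improvement to the uptake analysis and not a fault that undermines the study.

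**What to change.** In SAP 7.2:

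- Also measure SUVmean, SUVmax and the tumour/background ratio at the site of every malignant lesion on the centrally read conventional imaging that can be located on the PET/CT, whether or not a focus is seen.
- Name the SUV metric and the background region used for the ratio.
- State an exclusion for lesions that cannot be located or were treated since the conventional scan, and report how many were excluded.
- Present all-known-lesion and PET-visible summaries side by side by tumour type and GRPR status, with the share visible next to each.
- Give the GRPR-positive/negative SUV difference and its confidence intervals on both sets.

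No extra scan is needed: Protocol 4.1.6 already sends the conventional images to the central reader, and every PET has a low-dose CT. The costs are extra region placement, some localisation error on low-dose CT, and mean uptake that will look less favourable.
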